4.1 Main

- Confirm the usefulness and externally validate the scale.
- Compare this scale with other models of AKI prediction after cardiac surgery: Thakar, Mehta, ISR, Callejas, Leicester, CRATE.

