4.2 Secondary

- Identify new risk factors for Acute Kidney Injury (AKI)
- Understanding the incidence of AKI after cardiac surgery in Europe
- Validating a model for predicting discharge dialysis after cardiac surgery
- Investigate the performance of these models in specific surgeries: coronary surgery without cardiopulmonary bypass and heart transplantation.
- Assess the performance of other scales and compare them.
- Determine the prevalence and risk factors for Acute Kidney Disease (AKD) (renal injury beyond 7 days, up to 90 days).
- Determine the prevalence and risk factors for new Chronic Kidney Disease (CKD) (follow-up for 120 days or 4 months).
- Determine the prevalence and risk factors for CKD progression, defined by a one-stage progression in patients with pre-existing CKD. Follow-up for 120 days (4 months).

5. Methodology

5.1 Design: descriptive, observational, prospective, multicentre, prospective study.

5.2 Study population: patients undergoing cardiac surgery.

5.3 Ethical aspects: the study has been approved for assessment by the Ethical Committee for Research with Medicines of the Principality of Asturias.

5.4 Inclusion criteria: All patients over 18 years of age undergoing cardiac surgery.

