Serum potassium (mmol/L)
Serum chlorine (mmol/L)
Serum bicarbonate (mmol/L)
Lactate (mmol/L)

Urgent re-intervention first 24h

YES/NO

Length of hospital stay (days)

Discharge status

Discharge

Éxitus

Need for dialysis at discharge

YES/NO

Postoperative renal failure

Creatinine at ICU admission

Creatinine at 24h

Creatinine at 48h

Creatinine at 72h

Peak creatine 4th to 7th day

Peak creatine 7th to 14th day

Last creatinine at hospital discharge

Does the patient develops Stage 1 AKI in the first 14 days?

*Stage 1 AKI: (\uparrow) Creatinine 1.5-1.9 times baseline or ≥ 0.3 mg/dL increase

If yes, which day?

Does the patient develops Stage 2 AKI in the first 14 days?

*Stage 2 AKI: (\uparrow) Creatinine 2-2.9 times baseline

If yes, which day?

Does the patient develops severe AKI in the first 14 days?

* Stage 3 AKI : (\uparrow) Creatinine ≥ 3 times baseline or ≥ 4 mg/dL increase or dialysis.

If yes, which day?

Does the patient requires renal replacement therapy within the first 14 days?

If yes, which day?

5.7 Sample size estimation: Taking into account an incidence of moderate severe AKI in Spain of 9% according to previous studies and using the

Wilcoxon test, 1045 patients are needed to detect a difference of 0.1 in aROC with a power of 80% and an alpha error of 0.05. Assuming a 10% loss to follow-up, 1150 patients would be needed.

5.8 Data collection: a data collection notebook will be used to carry out the study. The researcher will include in it the sample of patients, without any data that would allow their identification.

5.9 Analysis of results: the results will be analysed using the statistical package IBM-SPSS 20.0 for Mac OS and RStudio version 1.1.463. The basic statistics of centralisation and dispersion will be used to describe the results. For comparison of means, t-tests for independent data or Mann-Whitney U-tests will be used in those cases where the conditions for their application are violated. Chi-square tests shall be used for comparison of proportions. Bonferroni correction shall be applied for multiple contrasts. To study the predictive ability, 2 measures will be studied, the discrimination ability by means of the area under the ROC curve and the calibration by means of the Hosmer Lemeshow Test. The areas under the ROC curve will be compared using the Mann-Whitney U test.

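### The Mann-Whitney U test named in section 5.9 does not test whether two scores have equal AUCs, so the score comparison that is a main objective has no valid test

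*Combined protocol and SAP*

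**What the plan says.** The second main objective in section 4.1 reads "Compare this scale with other models of AKI prediction after cardiac surgery: Thakar, Mehta, ISR, Callejas, Leicester, CRATE". With the index score, that makes seven scores. Section 5.1 describes a single observational cohort ("5.1 Design: descriptive, observational, prospective, multicentre, prospective study"), with no allocation of patients to scores.

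Section 5.9 measures discrimination ("the discrimination ability by means of the area under the ROC curve") and then says how scores are to be compared: "The areas under the ROC curve will be compared using the Mann-Whitney U test". The plan mentions no method for paired or correlated ROC curves. Two other sentences in 5.9 bear on the point:

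- Where group averages are compared, "t-tests for independent data or Mann-Whitney U-tests will be used in those cases where the conditions for their application are violated". Here Mann-Whitney has its ordinary independent-groups meaning.
- "Bonferroni correction shall be applied for multiple contrasts". The number of contrasts is not given.

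Section 5.7 bases the sample size on a Wilcoxon calculation and states: "1045 patients are needed to detect a difference of 0.1 in aROC with a power of 80% and an alpha error of 0.05". It does not give the reference AUC, any correlation between scores, or whether the test is one- or two-sided.

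**The concern.** The Mann-Whitney statistic divided by (cases × non-cases) is the empirical AUC of **one** score, and its test has the null hypothesis that this AUC is 0.5. It contains no second AUC and no covariance term. An analyst told to compare AUCs with it has to improvise, and no ordinary use of the test answers the question.

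What is at stake is the inference for a main objective. Two equally discriminating scores could be reported as different because one predicts higher risks overall, or a true difference of 0.1, the size named in section 5.7, could be missed.

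**Working it through.** **Inputs from the plan.** N = 1045 before losses, incidence 9%, AUC difference 0.1, power 80%, alpha 0.05 (section 5.7); seven scores (4.1); Mann-Whitney and Bonferroni (5.9). Expected cases: 0.09 × 1045 = 94.05; non-cases: 950.95.

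**Assumptions.** The plan gives neither AUC levels nor correlations. I used AUCs of 0.70 to 0.80 and score correlations of 0 to 0.7. Pairing is inferred from the single-cohort design.

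**1. The plan's own figure.** Noether's formula for the Wilcoxon test (AUC 0.6 against 0.5) is

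N = (z_α + z_β)² / [12 c(1−c)(AUC − 0.5)²], with c = 0.09.

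- Denominator: 12 × 0.09 × 0.91 × 0.01 = 0.009828.
- Two-sided: (1.960 + 0.842)² / 0.009828 = 7.849 / 0.009828 ≈ 799.
- One-sided: (1.645 + 0.842)² / 0.009828 ≈ 629.
- Power at 1045, two-sided: Φ(√(1045 × 0.009828) − 1.96) = Φ(1.245) = 89%.

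So 1045 is not reproduced by that route. Formulas for two AUCs give 267 to 1678, depending on the unstated lower AUC, correlation and sidedness. One choice comes close: 0.80 against 0.90, uncorrelated, two-sided, gives 1034. The figure is therefore neither confirmed nor shown to be wrong, and the fault in 5.9 does not depend on it.

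**2. What each reading of the sentence tests.** Binormal simulations, N = 1045, 9% cases, 500 to 1000 runs per scenario. Score correlation is 0.5 unless stated.

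| Use of the test | True state | Rejects | Paired DeLong rejects |
|---|---|---|---|
| AKI vs no AKI, within each score | AUCs 0.75 / 0.75 | 100% for both scores | 4-5% |
| Same | AUCs 0.80 / 0.70 | 100% for both scores | 95% |
| Score A vs score B, all patients | Equal AUCs 0.80, mean risks 8.6% vs 2.8% | 100% | 4.5% |
| Same | Equal AUCs 0.75, one score shifted 0.3 SD | 100% | about 5% |
| Same | Equal AUCs 0.75, same scale | 0.3-0.6% | 4-5% |
| Same | AUCs 0.70 / 0.80, same risk scale | 0% | 96% |
| Same, second set-up (correlation 0 to 0.5) | AUCs 0.80 / 0.70, no shift | 3-10% | 77-95% |
| Score A vs score B, cases only | Equal AUCs 0.75, one score shifted 0.3 SD | 49% | about 5% |

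The within-score test rejects for both scores whether or not their AUCs differ. The between-score test follows the scale of the scores. A monotone shift leaves an AUC unchanged, so rejection there says nothing about discrimination.

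**3. Comparing the two AUCs as if independent.** The variance of the difference is

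Var = V₁ + V₂ − 2r·SE₁·SE₂,

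where r is the correlation between the AUC *estimates*. The Hanley-McNeil variance, with Q₁ = A/(2−A) and Q₂ = 2A²/(1+A), is

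V = [A(1−A) + (n₁−1)(Q₁−A²) + (n₀−1)(Q₂−A²)] / (n₁n₀).

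- A = 0.70: V = 0.000971, SE = 0.0312.
- A = 0.80: V = 0.000785, SE = 0.0280.
- SE of the difference: √(0.000971 + 0.000785) = 0.0419 at r = 0; √(0.001756 − 0.000873) = 0.0297 at r = 0.5.

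Ignoring r = 0.5 therefore inflates the standard error by a factor of about 1.41. With equal AUCs the true variance is 2V(1−r), while the unpaired test uses 2V. Its type I error is then 2[1 − Φ(1.96/√0.5)] = 2[1 − Φ(2.77)] = 0.6%.

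Simulation with score correlation 0.5 agrees: 0.5-1% type I error. Power is 84-85% unpaired against 95-96% paired for 0.70 vs 0.80. For 0.75 vs 0.80 it is 23% against about 50% (51% in one set-up, 49% in the other).

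**4. With Bonferroni for six contrasts.** Alpha is 0.05/6 = 0.0083 and z = 2.638. By the formula in step 3, paired power for 0.70 vs 0.80 is Φ(0.1/SE − 2.638):

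- r = 0: Φ(2.386 − 2.638) = 40%
- r = 0.3: Φ(2.849 − 2.638) = 58%
- r = 0.5: Φ(3.365 − 2.638) = 77%
- r = 0.7: Φ(4.328 − 2.638) = 95%

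Simulated DeLong power at this alpha was 57%, 71%, 86% and 97% for *score* correlations of 0, 0.3, 0.5 and 0.7. The two sets differ because the variance model and the meaning of r differ.

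**The case against.** The best defence is that Mann-Whitney is loose shorthand. It is the U statistic behind the empirical AUC, DeLong's method is built on it, and the sentence directly follows the discussion of AUC and calibration. The text does not say this, however, and the same section uses the test in its ordinary sense as the alternative to an independent-samples t-test. An analyst following the plan would run the ordinary test.

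Second, the 100% and 0% figures come from comparing predicted risks, whereas 5.9 speaks of comparing areas. They depend on assumed scales, and the second set-up gave 3-10% where the first gave 0%. This stands as a limit on the illustrations.

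Third, if the areas themselves are compared as independent, the error is conservative. For score correlations of 0 to 0.7, the unpaired test rejected equal AUCs in 0-4% of runs and kept 81-88% power for 0.70 vs 0.80 at unadjusted alpha. This also stands: on that reading the harm is lost power, with no excess of false positives. Under Bonferroni for six contrasts, unpaired power falls to about 53-56%.

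Fourth, 5.7 does not say that its 0.1 difference is between two scores, and a Wilcoxon calculation is coherent for one AUC against 0.5. That is fair, so the link to 5.7 is secondary. The AUC estimates and the external validation of the index score are unaffected.

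**Conclusion.** The concern holds. The only test named for the second main objective does not have equality of two AUCs as its null hypothesis, and it makes no allowance for scores measured on the same patients. That follows from the definition of the test and from the single-cohort design; it needs no numerical assumption.

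The size of the damage depends on the reading. Used between scores, the test can reject in every run when discrimination is equal, and in 0-10% of runs when the AUCs differ by 0.1. Used as an unpaired AUC comparison at score correlation 0.5, it costs about 11 percentage points of power for 0.70 vs 0.80. These figures rest on assumed AUCs, scales and correlations, binormal scores, and alpha 0.05 before Bonferroni. Bonferroni adjusts the significance level and does not repair the wrong null. The sentence must be corrected before analysis.

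**What to change.** In section 5.9, replace the sentence with wording such as:

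> AUCs of scores computed on the same patients will be compared with the paired DeLong test for correlated ROC curves, or with a paired bootstrap. Each AUC difference will be reported with its 95% confidence interval.

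State that the primary contrasts are the index score against each of the six others, if that is the intention, so that the Bonferroni divisor is fixed. Because the study is multicentre, a bootstrap that resamples by hospital is a reasonable option; it is not essential to this correction.

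In section 5.7, restate the justification for the same paired comparison, giving the two assumed AUCs, their correlation, the sidedness and the number of contrasts.

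Cost: the 5.9 change is wording only. It runs in R, which the plan already uses, and needs no new variables or patients. Restating 5.7 could show that 1045 is ample or short: with six contrasts and 0.70 vs 0.80, power falls below 80% at low correlation. That is better known before the data are analysed.

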5.10 Limitations of the study

Those due to the prospective study design and those arising from the impossibility of reviewing the patients included in the database.

5.11 Timeline

- Completion of the project protocol and application to the ethics committee: February-March 2023
- Completion of the database: from obtaining the ethics committee to completing the sample size:

6-12 months

- Statistical analysis: 2 months
- Project drafting: 6-12 months

6. Ethical aspects

This study will follow the ethical principles set out in the Declaration of Helsinki, the Council of Europe Convention on Human Rights and Biomedicine and the Unesco Universal Declaration on the Human Genome and Human Rights. In addition, it will comply with the requirements of Spanish legislation in relation to biomedical research, personal data protection and bioethics. To ensure its approval, it will be submitted to the Research Ethics Committee (EC) and only patients who have signed an informed consent form will be included. Confidentiality and data security will be maintained in the following areas

The research manager will be responsible for maintaining the records at each site and determining the publication policy.

7. Dissemination of research results and substudies

The Scientific Committee will appoint an Editorial Committee to prepare the scientific report(s) of this research, which will be disseminated in due course. A number of secondary analyses are expected to be carried out, the conduct of which will be prioritised by the investigators and they will be encouraged to carry them out. Participation in these analyses will be based on the contribution to the study in their respective fields. The Steering Committee, before granting any application, will consider both the scientific validity and the possible impact on the anonymity of the participating centres. If required, the terms of collaboration will be established in advance by written agreement. The approval of the final version of all manuscripts, prior to submission, rests with the Scientific Committee. In case of disagreement within the Steering Committee, the Head of Research will make the final decision.

8. Data management and ownership

The study sponsor will act as the data custodian. In accordance with the principles of data preservation and data sharing, the Steering Committee, following publication of the overall database, will consider all reasonable requests for secondary analyses. The quality and validity of any proposed analysis shall be the main criteria to be taken into account when deciding on such requests. Only summary data will be publicly disclosed and it will be ensured that all data at international, national, institutional and patient level will be strictly anonymised. Patient data provided by participating hospitals are the sole property of their respective institutions. Once each local coordinator has confirmed the completeness and accuracy of the data provided by their hospital, the data will be transferred to a general database. The complete dataset of the participants will be coded for patients, hospitals and communities, and will be made freely available to the public for two years from the publication of the main scientific report. Prior

to this deadline, the Scientific Committee will not be obliged to release the data to any collaborator or third party if it considers that this does not align with the broader objectives of the project. All identifiable data collected, processed and stored for project purposes will be kept confidential at all times and will comply with Good Clinical Practice for Research (GCP) guidelines and the General Data Protection Regulation (GDPR) EU Regulation 2016/679.

9. Privacy and use of clinical information

The processing, communication and transfer of data will be carried out in accordance with the provisions of Regulation (EU) 2016/679 of the European Parliament and of the Council of 27 April 2016 on the protection of individuals with regard to data processing and the free movement of data, and the Ley Orgánica 3/2018, de 5 de diciembre, de Protección de Datos Personales y garantía de los derechos digitales.

10. Legal and organisational aspects.

10.1 Trial funding The study is not currently funded.

10.2 Compensation Neither trial sites, investigators nor patients will receive financial compensation.

11. Bibliography

